## **RESEARCH DESIGN AND METHODS**

Briefly describe study design and anticipated enrollment, i.e., number of subjects to be enrolled by researchers study-wide and by Partners researchers. Provide a brief summary of the eligibility criteria (for example, age range, gender, medical condition). Include any local site restrictions, for example, “Enrollment at Partners will be limited to adults although the sponsor’s protocol is open to both children and adults.”

This is an investigator-initiated study looking at the effects of the Bioboosti device on sleep for patients who have been diagnosed with insomnia and chronic migraine (15 or more headache days per month according to the International Classification of Headache Disorders III-Beta). We will screen

and enroll patients with insomnia and chronic migraine who are  $\geq 18$  years old for consistency on sleep data and age range. The study protocol consists of enrollment; baseline sleep and headache assessment, actiwatch use and set up of EEG; removal of the EEG then two weeks of treatment with Bioboosti; a post-treatment sleep assessment followed by a final visit to remove the EEG.

Adult patients  $\geq 18$  years old seen in the BWH and FH sleep and headache clinics are eligible for participation in the study. As we are unsure of the effects that the Bioboosti has on the general population, and in turn the various effects of chronic conditions on a person's sleep, we will exclude patients with known untreated moderate or severe sleep apnea, or with major circadian rhythm disorders, as these may confound our analyses. We will also exclude patients who are pregnant or breastfeeding; patients with cardiac pacemaker; any electrical devices; patients with cancer; patients with severe conditions related to heart, brain, kidney and hematopoietic system; patients with severe/unstable angina pectoris, arteria coronaria/peripheral arterial bypass graft, congestive heart failure, renal insufficiency, mechanical intestinal obstruction. Subjects with medication overuse headache defined as using specified abortive medications 9 or more days per month will also be excluded. Abortive medications for the purposes of this study will include opioids, combinations analgesics (barbiturates and/or caffeine contain medications), and triptans.

We anticipate enrolling 20 subjects at Brigham and Women's and Faulkner Hospitals.

We do not anticipate all 20 subjects to participate however, interested enrolled subjects will also be offered to continue the treatment for one year for the evaluation of sustained efficacy of BioBoosti as Insomnia Treatment. We *anticipate* enrolling up to 20 subjects at BWH and Faulkner Hospitals.

The study will also look at the effects of the BioBoosti device on sleep and recurrence of headache for patients who have been diagnosed with both insomnia and migraine. The study protocol remains the same besides the treatment with BioBoosti will be for 4 weeks to allow adequate headache assessment.

We anticipate enrolling 20 additional subjects with insomnia and comorbid migraine at Brigham and Women's and Faulkner Hospitals.

Briefly describe study procedures. Include any local site restrictions, for example, "Subjects enrolled at Partners will not participate in the pharmacokinetic portion of the study." Describe study endpoints.

The BWH and FH sleep clinics will be screened for follow-up patients with insomnia. Study staff will notify the treating physician to inform them of a potential subject. The treating physician will first introduce the study to the potential subject. If the subject gives permission and would like to obtain more information regarding the study, study staff will approach them and provide them with a copy of the consent form to review. Study staff may also contact the subject by phone to explain the study and recruit if it is more convenient for the subject. Study staff and a physician investigator will be available to answer all questions. If the potential subject is interested in participating in the study, the Principal Investigator will consult with the treating physician prior to enrolling the subject. If the subject decides to enroll in the study when approached in the clinic, we will proceed with Visit 1 (Enrollment Visit) that same day. The physician investigator will be available to speak with subjects during the consent process.

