**VERSION DATE**

**06/04/2018**

**SPECIFIC AIMS**

Concisely state the objectives of the study and the hypothesis being tested.

**Hypothesis 1:** Patients with insomnia have longer, more consolidated sleep after treatment with Bioboosti.

**Specific Aim 1:** This hypothesis will be tested in a prospective study, using within subject comparisons, whereby sleep measures before treatment are compared to those after treatment.

**Hypothesis 2:** Sleep improvement will lead to a lesser subjective daytime sleepiness and reduction in migraine frequency/intensity.

**Specific Aim 2:** This hypothesis will be tested by comparing subjective measures of sleepiness, measured by standard instruments (Epworth sleepiness scale score, ESS, Karolinska sleepiness scale KSS), relative to total sleep time and wake after sleep onset. Migraine frequency and intensity will be recorded using standardized headache diaries.

**Exploratory aim:** To evaluate the physiological mechanisms, by which Bioboosti may exert its effect on sleep and overall health. This will be accomplished by a measurement of hormones directly affecting sleep and

sympathetic autonomic nervous system (urinary cortisol and catecholamines), immune, as well as autonomic function.

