### **Arm 1**

**Aim 1:** To test the hypothesis that treatment with BioBoosti has sustained efficacy in treating insomnia.

Our primary endpoint would be insomnia symptoms after 1 year of BioBoosti use as compared to initial symptoms (prior to starting treatment).

Measurement of insomnia will be done in serial comparisons every 3 months for ISI, TST (Total Sleep Time), WASO (Wake After Sleep Onset), as well as PSQI at year 1. We will use repeated measures ANOVA to compare ISI, TST, WASO, at months 3, 6, 9, and 12 and a T-test to compare PSQI at baseline to that after 1 year.

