### **Arms 2**

**Aim 2:** To test the hypothesis that patient with Insomnia and comorbid Migraine will have longer, more consolidated sleep with lesser migraine frequency/intensity after treatment with BioBoosti.

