## **BACKGROUND AND SIGNIFICANCE**

Provide a brief paragraph summarizing prior experience important for understanding the proposed study and procedures.

Insomnia is a leading health complaint, seen in almost 25% of the population. Insomnia complaints can be associated not only with discomfort for the patient, but also with loss of productivity, poor health, and a higher healthcare utilization. Insufficient or poor quality sleep increases the risk of a variety of disorders, leading to abnormalities of endocrine (Buxton, Pavlova et al 2010) and immune function (Lange et al 2011). Insomnia probably has the some of the same consequences as insufficient sleep from other causes. For example, in a recent study in our group (Buxton, Pavlova et al, 2011), we found that sleep fragmentation, as measured by wake after sleep onset (WASO), predicts diabetes risk in insomnia patients.

Treatment of insomnia is particularly challenging among patients with comorbidities, where insomnia is also more common. For example, insomnia is seen in 40-51% of patients with epilepsy (Vendrame 2013, Lopez et al 2013). Many studies indicate that patients with epilepsy frequently have fragmented sleep, as well as excessive daytime somnolence (Holoway et al 2011, Meyer et al 2011, Manni et al 2010, Krishnan et al 2012). Yet treatment of insomnia in these patients is very challenging, as many of the

frequently used medications may interact with antiepileptic medications, or affect seizure threshold. For example, benzodiazepines, which are among the most commonly used of treatment of insomnia, can be associated with withdrawal seizures, and are particularly risky in these patients. Similar considerations exist for the patients with cardiac disease and dementia. For example, although long term benzodiazepine use can be associated with frequent falls (Berry et al, 2015), impaired memory (Billioti et al, 2015) and even all-cause mortality (Iennum et al, 2015), they are frequently prescribed and needed. From a recent review (DeFrancesco, et al, 2015) it can be inferred that every fifth patient with Alzheimer’s disease will need benzodiazepine treatment.

Sleep disturbances can serve as a trigger for migraines, and insomnia in particular is a common comorbidity in patients with chronic migraine. Addressing insomnia in patients with chronic migraine can result in reductions in migraine frequency (Smitherman, et al, 2016)

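### The opening eligibility text of Research Design and Methods requires chronic migraine for the two-week, 20-subject study, which conflicts with the schedules and recruitment text that treat that cohort as insomnia patients; eligibility should be restated by cohort

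*Combined protocol and SAP*

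**What the plan says.** **Opening of Research Design and Methods.** The study is for "patients who have been diagnosed with insomnia and chronic migraine (15 or more headache days per month", and staff will screen and "enroll patients with insomnia and chronic migraine who are" adults. The sequence given for these patients includes "removal of the EEG then two weeks of treatment with Bioboosti", and the anticipated enrolment is 20. The same text mentions a headache assessment at baseline, names headache clinics alongside sleep clinics as a source, and excludes medication-overuse headache.

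**Later paragraphs of the same section.** Enrolled subjects who are interested, up to 20, may continue for one year. The study will also look at patients with both insomnia and migraine, treated for 4 weeks, with 20 additional subjects.

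**Visit schedules.** There are two. The one headed For Insomnia has two weeks of treatment, refers to 20 participants, and collects sleep logs but no headache diary. The one headed For Patients with Insomnia and Migraine has one month of headache diaries before treatment and one month of treatment.

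**Recruitment Procedures and Consent Procedures.** Both list two groups: patients with insomnia, and patients with both conditions.

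**Aims.** Hypothesis 1 is that "Patients with insomnia have longer, more consolidated sleep after treatment with Bioboosti". Arm 1 says "Our primary endpoint would be insomnia symptoms after 1 year of BioBoosti use as compared to initial symptoms". Arms 2 concerns the hypothesis that a "patient with Insomnia and comorbid Migraine will have longer, more consolidated sleep with lesser migraine frequency/intensity" after treatment.

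**The concern.** The opening text answers the protocol template's request for a summary of eligibility, so staff would look there to decide who may enter. It names a single population, insomnia with chronic migraine, and attaches to it the duration and sample size that the rest of the protocol gives to the insomnia cohort.

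Whichever reading is followed, something goes wrong:

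- If staff apply the opening text, patients with insomnia alone are turned away. Hypothesis 1 and the one-year endpoint, which is measured in enrolled subjects who continue, would then be studied only in patients who also have migraine.
- If staff follow the schedules and the recruitment text, every two-week subject without chronic migraine falls outside the written enrolment rule.

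The migraine definition also varies. The opening text requires chronic migraine with a headache-day threshold. Arms 2, the later paragraphs of Research Design and Methods, the migraine schedule heading, and the recruitment and consent sections say only migraine.

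**Working it through.** The protocol gives no alpha, power, effect size, standard deviation or dropout rate. The two figures of 20 therefore cannot be reproduced, and no sample-size formula applies. The check is a comparison of the text and a count of places.

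**Step 1. Which cohort does the opening text describe?**

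| Feature | Opening of Research Design and Methods | For Insomnia schedule | Migraine cohort (later paragraphs and own schedule) |
|---|---|---|---|
| Population | Insomnia and chronic migraine | Insomnia | Insomnia and migraine |
| Treatment | Two weeks | Two weeks | 4 weeks, or one month |
| Subjects | 20 | 20 | 20 additional |
| Headache content | Baseline headache assessment; medication-overuse exclusion | No headache diary | Headache diaries before, during and after treatment |

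Duration and size match the insomnia cohort. Population and headache content match the migraine cohort. The likeliest explanation is that migraine-cohort wording was merged into the two-week paragraph.

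**Step 2. Places open to insomnia without migraine.**

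Implied total: 20 + 20 = 40. This is a sum; the protocol does not print it. It treats the up-to-20 figure as the one-year continuation of subjects already enrolled.

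- Opening text read literally with the later paragraphs: 0 of the first 20 + 0 of the additional 20 = 0 of 40.
- Schedule headings, recruitment and consent sections: up to 20 of the first 20 + 0 of the additional 20 = up to 20 of 40, and 20/40 = 50%. It is *up to* because nothing in those sections bars a two-week subject from also having migraine.
- One-year phase, up to 20 continuing subjects: 0 on the literal reading, up to 20 on the other.

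**Step 3. Sensitivity to the reading of the one-year figure.** If the up-to-20 were new places, the total would be 20 + 20 + 20 = 60. They would still come from the population in the opening text, so the literal count stays at 0. Only the denominator moves.

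**Step 4. Which sections carry the evidence?** The weight rests on the two schedule headings, the separate 20 additional subjects, and the recruitment and consent text. Several visit descriptions do not restate a population and count only because of the heading above them. Specific Aims states hypotheses, not cohorts, and its Aim 2 says "Migraine frequency and intensity will be recorded using standardized headache diaries" without assigning this to a cohort. The Sustained Efficacy Phase hands out headache logs without setting an entry condition.

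**Step 5. Which migraine definition applies to the second cohort?** The later paragraphs say its protocol is otherwise unchanged apart from treatment length, and Background and Significance says "Addressing insomnia in patients with chronic migraine can result in reductions in migraine frequency". Both point towards chronic migraine. The threshold is not repeated where the cohort is described, so the definition remains open.

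**The case against.** The strongest reply is that the intent can be recovered. There are two schedules and two recruitment groups. The migraine schedule justifies its longer testing period by experience so far in individuals with insomnia, which suggests that the first cohort was already running as an insomnia cohort. The opening text also has a sentence making adults seen in the sleep and headache clinics eligible, with no migraine condition. On this view the count of 0 measures an editing slip, not a bias or a loss of power.

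Much of this stands. It is why the point is graded as an inconsistency that should be fixed, and not as a flaw that invalidates the design. Two things remain. The clinic sentence does not mention insomnia either, so it cannot be the whole rule, and it does not cancel the enrolment sentence before it. And the headache content in the opening text, Aim 2 and the one-year phase means the protocol does not point in only one direction.

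Three stronger readings are tempting but not supported:

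- **That the trial plans to enrol no patients with insomnia alone.** That needs the opening and later paragraphs of one section to be read apart from the schedules and the recruitment text.
- **That Hypothesis 1 could not be tested.** Patients with insomnia and migraine still have insomnia, so the within-subject comparison could be made. What is limited is the population to which the result applies.
- **That subjects already treated were enrolled in breach of the protocol.** Their migraine status is not given.

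**Conclusion.** The inconsistency is real. As written, the enrolment rule in the opening of Research Design and Methods would exclude the insomnia-only patients for whom the two-week schedule and one of the two recruitment groups appear to be meant. Its size is 0 of an implied 40 places on the literal reading against up to 20 of 40 (50%) on the other, and 0 against up to 20 in the one-year phase. The total of 40 rests on reading the up-to-20 figure as continuation of enrolled subjects; the count of 0 does not depend on that.

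The probable cause is merged text. The consequence is for who may enter and for how far conclusions about patients with insomnia extend. Category: internal inconsistency. Severity: should be fixed.

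**What to change.** Reconcile the sections by restating eligibility in Research Design and Methods separately for each cohort.

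- **Two-week insomnia cohort (20 subjects).** State eligibility without the chronic-migraine condition. If the sponsor does intend that condition, change the For Insomnia heading and the recruitment and consent sections to match, and limit the conclusion to insomnia with chronic migraine.
- **Insomnia-and-migraine cohort (20 additional subjects).** Use one migraine definition throughout, chronic or any as the sponsor decides.
- **Medication-overuse exclusion.** Say to which cohort it applies. It appears in Research Design and Methods but not in the exclusions listed under Equitable Selection of Subjects.
- **Reporting.** Give the migraine status of two-week subjects where it is already documented. A headache-day classification should not be assumed for all of them, because their schedule has no headache diary.

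The cost is one wording amendment and a descriptive line in the report, with no added visits, procedures or subjects.

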### For Insomnia

#### **Visit 1**

Subjects who are interested in participating will sign the consent form. A screening physical exam will be done, and vital signs (blood pressure, heart rate, pulse rate, respiratory rate) will be measured. Pregnancy test will be done for women of childbearing potential.

Subjects will go home with sleep logs, which are subject records of when they go to sleep and wake up. They will also be given an actiwatch to wear, as an objective measure of sleep and wake periods.

#### **Visit 2**

Subjects will be scheduled for a follow up at FH.

Subjective sleep symptoms will be evaluated using validated instruments, including Pittsburgh Sleep Quality Inventory (PSQI), and severity of insomnia - Insomnia Severity Index (ISI), and daytime sleepiness Epworth Sleepiness Scale (ESS), and daily visual analog scale (Karolinska sleepiness scale, KSS).

Objective sleep assessment will be performed using ambulatory 72 hour EEG, using sleep montage per standard AASM criteria, and scored by a registered polysomnography technologist using AASM guidelines. If the subject expresses hesitation because of the 72 hour EEG, then a 48 hour EEG will be offered.

Assessment of sympathetic autonomic nervous system function will be done by measuring cortisol and catecholamine levels using standard assays.

Subjects will continue to wear the actiwatch and complete sleep logs daily.

### **Visit 3**

Subjects will return for the EEG to be removed. Subjects will be given a Bioboosti for the treatment phase and instructed on how to use it. The research assistant will be trained in person by a Bioboosti representative. Using the device as part of the training, the research assistant will learn the proper placement of the device on the hands, what the different buttons represent and how to properly charge it. He/she will in turn instruct the participants with this information. Subjects will continue to use the actiwatch.

### **Treatment phase**

There will be two weeks of treatment with Bioboosti. Subjects will be asked to use the device once a day, at approximately one hour prior to initiation of habitual sleep time. They will complete up to 6 therapy cycles. A therapy cycle consists of placing the Bioboosti on the Laogong point, which is located at the center of the palm. The device will remain there for 8 minutes, and this counts as 1 cycle. When the light on the device changes, it indicates that 8 minutes have passed, and a cycle is completed. The subject will then remove the device and replace it on the Laogong point of the other hand. The subject will repeat this up to 6 times, alternating the treatment cycles between one hand to another.

They will complete sleep logs for two weeks, as well as wear the actiwatch.

During this time, subjects should not drive while using the Bioboosti. They will also be advised to maintain a healthy lifestyle, as is done during clinic visits (light diet, regular exercise, smoking cessation, abstinence and sufficient sleep), but these are not terms of exclusion from the study.

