### **Visit 6**

Subjects will return the completed sleep/headache logs. They will return the actiwatch.

For studies involving treatment or diagnosis, provide information about standard of care at Partners (e.g., BWH, MGH) and indicate how the study procedures differ from standard care. Provide information on available alternative treatments, procedures, or methods of diagnosis.
--------------------------------------------------------------------------------------------------------------------------------------------------------------------------------------------------------------------------------------------------------------------------------------

This study does not involve diagnosis. Other than the Bioboosti, the Principal Investigator will not make changes to the patient's medication regimen. Other treatments that are available to treat insomnia include: healthy sleep hygiene, antihistamines and some prescription medicines like Ambien and Lunesta.

As an alternative to standard care, we are proposing to test the Bioboosti device as a possible safe, non-pharmacologic treatment option for insomnia.

Describe how risks to subjects are minimized, for example, by using procedures which are consistent with sound research design and which do not unnecessarily expose subjects to risk or by using procedures already being performed on the subject for diagnostic or treatment purposes.

Risks of participation may include fatigue from completing the questionnaires and feelings of unease answering questions. We will make every attempt to schedule and perform the tasks so as to reduce these risks. Subjects may refuse to answer any question that upsets them.

When wearing the ambulatory EEG, subjects may feel soreness or see reddening of the skin from the glue that is used. There is a risk that the cables could become wrapped around the neck, so they should tape the cables to their back when sleeping. A registered polysomnography technologist will administer the ambulatory EEG so as to minimize these risks.

Subjects may feel discomfort when wearing the actiwatch. The strap is adjustable for their comfort.

Collection of specimen data will be done as in routine care.

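### Lifestyle advice is scheduled only in the treatment phase and at no baseline visit, so the before-after change may include an effect of new or reinforced advice that cannot be separated from the device

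*Combined protocol and SAP*

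**What the plan says.** Specific Aim 1 defines the comparison as "using within subject comparisons, whereby sleep measures before treatment are compared to those after treatment". No concurrent control or sham group is described.

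The advice appears in the Treatment phase section for insomnia and again, in the same words, in the Treatment phase section for insomnia with migraine: "They will also be advised to maintain a healthy lifestyle, as is done during clinic visits". Its content, and the fact that following it is not required, are given as "light diet, regular exercise, smoking cessation, abstinence and sufficient sleep), but these are not terms of exclusion from the study".

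The visits before treatment are itemised in both arms, and none mentions the advice:
- **Visit 1:** consent, examination, vital signs, pregnancy test, actiwatch and logs ("Subjects will go home with sleep logs, which are subject records of when they go to sleep and wake up"). The migraine arm adds headache diaries.
- **Visit 2:** PSQI, ISI, ESS, KSS, ambulatory EEG, and cortisol and catecholamines. In the insomnia arm, "Subjects will continue to wear the actiwatch and complete sleep logs daily".
- **Visit 3:** EEG removal, and supply of the device with instruction in its use.

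Two other statements bear on the point. Under Research Design and Methods, recruitment is described as "The BWH and FH sleep clinics will be screened for follow-up patients with insomnia". The standard-of-care text after Visit 6 says "Other treatments that are available to treat insomnia include: healthy sleep hygiene, antihistamines and some prescription medicines like Ambien and Lunesta".

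**The concern.** A single-group before-after comparison attributes to the device everything that differs between the two periods. The plan as written schedules a behavioural prompt in the treated period and gives staff no instruction to deliver it earlier. One element, sufficient sleep, bears directly on total sleep time, which is a named outcome.

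The protocol applies the opposite principle elsewhere. In the migraine arm, subjects keep the abortive treatments they used in the run-in and are told not to start new therapies during treatment. No matching statement holds the lifestyle advice constant. The study procedures also list no record of whether the advice was given or followed, so an analysis could not adjust for it.

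At stake is attribution. A change produced partly by the advice would be read as a device effect on sleep, and in the second arm possibly on headache as well.

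**Working it through.** **Step 1. Where the advice falls relative to the measurements**

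| Stage (both arms) | Measurement | Advice listed? |
|---|---|---|
| Visit 1 | Baseline logs and actiwatch start | No |
| Visit 2 | Baseline questionnaires, EEG, assays | No |
| Visit 3 | EEG removed, device supplied | No |
| Treatment phase (two weeks, or one month with migraine) | Logs and actiwatch continue | Yes |
| Visit 4 | Post-treatment questionnaires, EEG, assays | Not repeated |

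The advice is scheduled after the baseline questionnaires and EEG and before their post-treatment counterparts.

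**Step 2. What the before-after change estimates**

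Expected change = device effect + effect of advice that is new or reinforced in the treated period + other changes over time.

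With one group, these terms enter only as a sum. If the advice was already fully in effect at baseline, the second term is zero. If some of it is new or reinforced, that term may differ from zero. The documents do not say which case applies.

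**Step 3. Illustration of size**

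The plan gives no significance level, power, effect size or SD, so there is no figure of its own to reproduce. It names tests only for the one-year phase: repeated-measures ANOVA, and a t-test for PSQI. The following is an illustration under stated assumptions.

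Inputs:
- n = 20, the anticipated enrolment in each part of the study (Research Design and Methods).
- Two-sided paired t-test at 0.05 (assumed).
- Device effect zero, and other changes over time zero (assumed).
- d = effect of the new or reinforced advice, in SDs of the paired change (assumed, 0 to 0.4).

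Formula: the test statistic follows a noncentral t distribution with n − 1 = 19 degrees of freedom and noncentrality d√n. The critical value is 2.093. The chance of significance is P(T > 2.093) + P(T < −2.093).

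| d | d√20 | Upper tail | Lower tail | Chance of a significant change |
|---|---|---|---|---|
| 0 | 0 | 0.025 | 0.025 | 5% |
| 0.1 | 0.447 | 0.062 | 0.009 | 7% |
| 0.2 | 0.894 | 0.133 | 0.002 | 14% |
| 0.3 | 1.342 | 0.246 | 0.001 | 25% |
| 0.4 | 1.789 | 0.397 | 0.000 | 40% |

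The result depends entirely on d, for which the documents give no value.

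**The case against.** The strongest reply is that this is unchanged usual care. The sentence speaks of maintaining a healthy lifestyle and says the advice is the same as that given at clinic visits. Recruits are described as follow-up patients of the sleep clinics. On that reading many subjects had heard the advice before baseline, the baseline already contains it, and the contrast between periods is close to zero. This largely stands, and it limits what can be claimed. It does not close the point. The recruitment and consent sections speak only of diagnosed patients, so earlier exposure is not assured for everyone. Even a repeat of familiar advice is a reminder scheduled in one period only.

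A reader might infer more than the documents support in three ways:
- **That the advice is withheld before baseline.** No passage says so. The visit lists are merely silent.
- **That the before-after change does combine advice and device.** It may. Whether it does depends on how much of the advice is new or reinforced, which is not stated.
- **That the advice is the sleep hygiene named as an available insomnia treatment.** The protocol never equates the two. The list is general, only one item concerns sleep directly, no technique is described, and following it is voluntary.

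It is also fair to say that in an uncontrolled pilot this is one contributor beside expectancy, regression to the mean and time, and possibly a small one. That affects its priority. It does not remove the case for a nearly free correction.

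**Conclusion.** The point holds in a limited form. In both arms the plan schedules lifestyle advice in the treatment phase and lists it at no study visit before or at baseline. A contribution from new or reinforced advice to the before-after change therefore cannot be excluded, and the within-subject comparison cannot separate it from the device.

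The size is unknown. With an inert device, the chance of a significant result runs from the nominal 5%, if the advice adds nothing new, to 40% if it adds 0.4 SD of the paired change. That range rests on an assumed two-sided paired t-test at 0.05, all 20 subjects analysed, no other change over time, and advice effects that have no anchor in the documents. The benign end is plausible for patients already advised in clinic. The change is still worth making, because the timing is avoidable and costs almost nothing to correct.

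**What to change.** Give the same advice, with its content unchanged and in standard wording, at Visit 1 in both arms. It should come before the baseline logs, actiwatch, questionnaires and EEG. If it is repeated in the treatment phase, use the same wording there. Record for each subject that it was given and when. Both compared periods then follow the same advice. Add a sentence to the analysis plan stating that any remaining effect of advice cannot be separated from the device.

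The cost is one sentence repeated at Visit 1 in each arm and one entry on the case report form, with no extra visit or subject. There are two small downsides. The before-after change may be somewhat smaller. Advice that acts slowly may also still carry over into the treatment phase, particularly in the insomnia arm, where the interval between Visits 1 and 2 is not stated (it is one month in the migraine arm). The change reduces one imbalance between the periods and does not replace a control arm.
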